**4. Purpose, hypothesis and key questions:**

The proposed study will examine the threshold for nicotine self-administration (NSA) using five different nicotine doses in young adult male and female non-dependent smokers (light and intermittent smokers or LITS). We propose a double-blind, placebo-controlled study that will enroll 195 individuals, targeting a total of 72 completers (36 male and 36 females). In each of the five experimental sessions, smokers will be randomly assigned to one of the five doses of nicotine (0.0125, 0.025, 0.05, 0.1 and 0.2 mg/70 kg). The highest dose, 0.2 mg/70 kg, corresponds to nicotine delivered by about one or two puffs of a cigarette. At the beginning of each experimental session, smokers will sample the assigned both the nicotine dose for that experimental session, and the placebo (saline) dose, followed by the opportunity to choose between nicotine and placebo for a total of ten choices over a 165-minute period. The main outcomes will be threshold dose (the minimum dose of nicotine that is self-administered more than placebo) and the slope of dose-response for nicotine self-administration (changes in nicotine self-administration per unit change in nicotine dose). We will also collect measures of nicotine intake (cotinine), nicotine clearance (3-hydroxycotinine (3-HC) / cotinine), and self-report drug effects.

The following questions will be addressed:

Aim #1: To assess the threshold reinforcing dose and dose-effect curve for IV NSA at low doses in young adult LITS.

Hypothesis #1A: The threshold reinforcing doses for IV NSA will be between 0.0125 to 0.1 mg/70 kg.

Hypothesis #1B: The dose-effect curve for NSA will differ between males and females with relatively flat curve in female smokers.

Aim #2: To assess the threshold and dose-effect curve for the positive and negative/aversive subjective effects of IV nicotine at low doses and its relationship to nicotine reinforcement.

Hypothesis #2 A: The threshold for the positive effects will be between 0.0125 to 0.1 mg/70 kg, for the negative/aversive effect it will be  $\geq 0.1$  mg/70 kg.

Hypothesis #2B: Nicotine reinforcement will be positively correlated with the positive and negatively correlated with the negative/aversive subjective effects of IV nicotine.

Exploratory Aims: To examine the influence of nicotine clearance rate on nicotine reinforcement threshold and dose-effect curve.

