## **7. Subjects:**

Inclusion criteria: 1) Female and male smokers, aged 18 to 35 years, who have been smoking for at least a year, and a life-time consumption of at least 100 cigarettes; 2) smoke more frequently than once a week and  $\leq 5$  cpd; 3) FTND score  $\leq 3$  indicating no or minimal evidence for nicotine dependence; 4) urine semi-quantitative cotinine levels  $> 100$  ng/mL indicating an active smoking status; 5) not seeking treatment at the time of the study for nicotine dependence; 6) in good health as verified by medical history, screening examination, and screening laboratory tests; 7) for women, not pregnant as determined by pregnancy screening, nor breast feeding, and using acceptable birth control methods.

Exclusion criteria: 1) history of major medical illnesses that the physician investigator deems as contraindicated for the subject to be in the study; 2) requirement of any form of regular psychotropic medication (antidepressants, antipsychotics, or anxiolytics) or psychiatric diagnosis and treatment for psychiatric disorders including major depression, bipolar disorder, schizophrenia in the past 6 months; and 3) current dependence to alcohol or any other recreational or prescription drugs and; 4) daily use of smokeless tobacco products or exclusive daily use of e-cigarettes (non-daily users will be included).

Justification for age criteria: The study will enroll young adults between the ages of 18 to 35 because this age group represents a critical time for development of nicotine addiction, with almost all progression to daily smoking completed by the age of 26.

Stratified sampling procedure for race and presence of daily smoking: The study will enroll 36 male and 36 female LITS. The two groups will be matched on race and presence of daily smoking. Race has been shown to influence smoking behavior and nicotine pharmacokinetics. We will create a race variable (0= Caucasian, 1= African-American, 2=Other) to match groups on race. We will also stratify for the presence of daily smoking because daily smoking may influence the behavioral effects from smoking by tolerance development (9-11). This approach will allow balancing the male and female smokers for light vs. intermittent smokers. A categorical variable will be created for the presence of daily smoking (1= present, and 0 = absent).

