## **9. Selection:**

Male and female smokers will be recruited from the New Haven area through newspaper advertisements and fliers. We will recruit both veterans and non-veterans since there are not enough veterans in our area who meet the inclusion criteria for the study. Interested subjects will have the study described over the telephone and will be asked to answer a brief tobacco use history and medical screening questionnaire. If subjects are eligible for the study based on the telephone screening, they will then be invited to come to the clinic for an initial screening evaluation. The initial screening evaluation will include the following: a) obtaining an informed consent; b) smoking history and assessment of nicotine dependence based on the Fagerstrom Test of Nicotine Dependence (FTND); and c) a urine semi-quantitative cotinine level to confirm active smoking status at study entry..

If subjects are eligible based on the stratification procedure, they will be invited to participate in a second evaluation, which will include: a) complete physical and psychiatric examination including the structured clinical interview (SCID) for DSM-V; b) laboratory examination including CBC, ALT, AST, alkaline phosphatase, glucose, BUN, creatinine c) DNA; d) urine analysis, drug screening, and for women, urine pregnancy test. The laboratory test results will be part of the patients' medical record at the VA Hospital located on the CPRS system, as well as in the subject's research chart; and e) ECG.

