## **12. Data analysis methods:**

Data analyses: The primary analyses will be intent-to-treat and will include all available data on subjects who complete at least one test day. Mixed-effects models will be used to test the study hypotheses. These models allow for different numbers of observations per subject, use all available data on each subject, and are unaffected by randomly missing data. They also provide flexibility in modeling the correlation structure of the data. All data will be checked for normality and transformations will be applied as necessary. Significance level of 0.05 will be used for the main hypotheses and Bonferroni correction will be applied for post-hoc tests and secondary analyses.

Specific Aim #1: Aim #1: To assess the threshold reinforcing dose and dose-effect curve for IV NSA at low doses in young adult LITS. Hypothesis #1A: The threshold reinforcing doses for IV NSA will be between 0.0125 to 0.05 mg/70 kg. Hypothesis #1B: The dose-effect curve for NSA will differ between males and females with relatively flat curve in female smokers.

**Aim #1 Analysis:** The reinforcing effects of nicotine will be determined by the number of IV NSAs in each session, ranging from 0 to 10. The threshold dose for NSA will be determined by the lowest dose of nicotine for which the number of NSAs is significantly greater than those for placebo (saline) (i.e., proportion of NSA significantly higher than 0.5). For assessing the dose-response relationship, the parameters of interest will be the slope and shape of the dose-response curve. The slope indicates the degree to which self-administration changes with an increase in nicotine dose (in other words, sensitivity of NSA to changes in nicotine dose).

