We expect to observe a significant dose effect and will compare the proportion of NSAs at each dose to 0.5 across subject groups. The lowest nicotine dose that has a significantly higher proportion of NSA than 0.5 will be selected as the threshold dose (Hypothesis 1A). To assess the dose-response relationship in the preference for nicotine, polynomial effects of dose (linear, quadratic, cubic) and change-point linear models will be tested in the mixed effects logistic regression model. We anticipate that there will be a significant linear relationship between dose and response rate at lower doses with flattening of the relationship at higher doses. We will use the slope of the dose effect to assess the linear dose effect. Alternative non-linear dose response relationships will be considered if residual plots reveal significant deviations of the models from linearity. Gender differences in the shape of the curve for NSA will be examined in the logistic regression model by including gender main effect and its interactions with dose (Hypothesis 1B). Significant interactions between the group factors and dose will be considered supportive of systematic group differences in the dose-response relationships between groups. If significant interactions are observed, then separate thresholds and curves will be estimated within each subject group.

**Specific Aim #2:** To assess the threshold and dose-effect curve for the positive and negative/aversive subjective effects of IV nicotine at low doses and its relationship to nicotine reinforcement. Hypothesis #2 A: The threshold for the positive effects will be between 0.0125 to 0.1 mg/70 kg, for the negative/aversive effect it will be  $\geq 0.1$  mg/70 kg. Hypothesis #2B: Nicotine reinforcement will be positively correlated with the positive and negatively correlated with the negative/aversive subjective effects of IV nicotine.

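### Race and daily smoking are matched between the sexes by design but left out of every model that compares the sexes

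*Combined protocol and SAP*

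**What the plan says.** Section 7 (stratified sampling procedure) sets up the comparison of the sexes. "The study will enroll 36 male and 36 female LITS", and "The two groups will be matched on race and presence of daily smoking". The reasons are given there: "Race has been shown to influence smoking behavior and nicotine pharmacokinetics", and "We will also stratify for the presence of daily smoking because daily smoking may influence the behavioral effects from smoking by tolerance development". Race is coded 0/1/2 and daily smoking 0/1.

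Section 9 places the stratification between the initial screening and the full examination: "If subjects are eligible based on the stratification procedure, they will be invited to participate in a second evaluation".

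Section 12 (Aim #1 Analysis) fits a mixed logistic model with dose as a fixed categorical term and subject as a random effect. Sex is examined "by including gender main effect and its interactions with dose". Aim 2A explores gender in the same way. Aim 2B uses the subjective effect, dose, gender and their interactions. The analysis "will include all available data on subjects who complete at least one test day".

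Race and daily smoking appear nowhere in Section 12. Its plural reference to group factors names only gender. Section 11C announces estradiol and progesterone as covariates in women, and a depression scale to control for baseline differences, but not the two matching factors.

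**The concern.** Sex cannot be randomised, so for these two factors the matching in Section 7 is the only stated protection for the sex contrast. The protocol does not describe the kind of matching (individual or frequency), its tolerance, or how balance is maintained when subjects fail the second evaluation, drop out or are replaced. Any imbalance that remains goes unadjusted into the sex comparison.

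Hypothesis 1B is one of the main hypotheses. Its interaction test also decides whether thresholds and curves are estimated separately by sex. The protocol's own argument about tolerance is a reason to think that daily smoking could change the dose curve as well as its level. Settling the covariates now also avoids choosing them after the baseline table has been seen.

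**Working it through.** **The plan's own figure.** Section 12 states 80% power for 67% (two-thirds) against 50% with 72 subjects, two-sided 0.05. An exact binomial test rejects at 45 or more of 72 (upper tail 0.0222 under 0.5) and has power 0.810 at two-thirds. The second figure, d = 0.34 with n = 72, gives 0.812 by a one-sample t test. Both are reproduced. Neither calculation contains sex, race or daily smoking, so the fix leaves them unchanged.

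**Precision of the sex main effect.** The inputs are assumed, on the linear proportion scale. With between-subject variance su2, within-session variance se2 and five sessions, the relative fall in standard error is

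1 - sqrt[(su2(1 - R2) + se2/5) / (su2 + se2/5)]

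- su2 = 0.01, se2 = 0.05: R2 = 0.10 gives 1 - sqrt(0.019/0.020) = 2.5%; R2 = 0.20 gives 1 - sqrt(0.018/0.020) = 5.1%.
- su2 = 0.03, se2 = 0.06: R2 = 0.10 gives 1 - sqrt(0.039/0.042) = 3.6%; R2 = 0.20 gives 1 - sqrt(0.036/0.042) = 7.4%.

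**Bias of the sex main effect.** Shift = imbalance x effect. If the share of daily smokers differs by 10-20 points and their preference differs by 0.10-0.20, the shift runs from 0.10 x 0.10 = 0.01 to 0.20 x 0.20 = 0.04.

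The documents give no figure for imbalance. As a device, suppose 36 balanced subjects per sex plus m others per sex, among whom the daily-smoking share differs by g. The overall gap is m x g / (36 + m). For g = 0.20 to 0.60 it is 2.4-7.3 points (m = 5), 4.3-13.0 (m = 10) or 7.1-21.4 (m = 20). A 10-20 point gap therefore needs many such subjects and a large difference among them.

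**The sex-by-dose test.** A subject's race or daily-smoking main effect is the same at every dose, so it largely cancels from within-subject dose contrasts. Bias needs imbalance and a factor-by-dose interaction together. An illustrative simulation used no true sex effect, a random-intercept SD of 1 on the logit scale, five equally spaced dose steps, 1-4 sessions for each of the m extra subjects, and logistic regression with cluster-robust errors in place of the mixed model. With 500 runs, rejection rates are good to about 2 points. The table shows the unadjusted model; biases are in logits.

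| m per sex; daily share among them | Daily effect; daily x dose | Sex bias; rejection | Sex x dose bias; rejection |
|---|---|---|---|
| 0 | 0.5; 0.2 | -0.006; 5.8% | 0.003; 3.4% |
| 10; 70% v 30% | 0.5; 0 | -0.017; 4.6% | 0.001; 4.0% |
| 10; 70% v 30% | 0.5; 0.2 | -0.022; 5.4% | -0.010; 5.2% |
| 20; 80% v 20% | 0.8; 0.3 | -0.078; 6.6% | -0.029; 7.6% |

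In the last row, adding the daily-smoking main effect alone reduces the sex bias to 0.006 but leaves the sex-by-dose bias at -0.030. Adding daily smoking by dose brings the latter to 0.003 (rejection 6.2%).

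**The case against.** A reader might infer, from the completer target of 36 and 36 in Sections 4 and 10 and the one-test-day rule in Section 12, that the set analysed is not the matched set. The documents do not support this. Section 7 ties the matching to enrolment and Section 9 applies the stratification before the second evaluation, so everyone analysed has passed it. Sections 4 and 10 state a completer target without mentioning matching. If matching is at entry, keeping everyone with at least one test day preserves more of it than a completers-only set would. Section 10 reports 23 completers among 45 consented under the previous design, but that may include screen failures and subjects still in progress, so it is not a dropout rate after dosing.

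Other objections stand in part:

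- The precision gain and the 0.01-0.04 shift concern the sex main effect, whereas Hypothesis 1B is about sex by dose. This is correct, and it limits the point.
- The shift range may be high. Dividing the simulated logits by 4 (valid near a proportion of 0.5) gives 0.022/4 = about 0.005 and 0.078/4 = about 0.02.
- The subject random intercept already absorbs between-subject variance, so the precision argument does not reach the within-subject test.
- Interaction terms use parameters, and race cells may be sparse. This favours a sensitivity analysis over the primary model for those terms.

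None of this explains why factors judged important enough to match on are absent from the models.

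**Conclusion.** The point holds as a gap between design and analysis: the matching factors are in no model that contains sex, and the protocol is silent on how balance is maintained. Adjustment protects the sex main effect and, if the factors explain 10-20% of between-subject variance, lowers its standard error by about 3-7%. That range rests on assumed variances and a linear approximation to a logistic model.

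It would be tempting to go further and say that the Hypothesis 1B test is confounded. The documents give no evidence of imbalance or of a factor-by-dose effect. In the simulation the sex-by-dose bias was negligible when the groups were balanced, and it reached -0.029 logits with 7.6% rejection only under extreme assumptions. The expected effect on Hypothesis 1B is small. Low priority.

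**What to change.** In Section 12, state that race (three categories) and daily smoking (0/1) enter as fixed effects in every model that includes sex, whatever their significance. This costs 2 + 1 = 3 parameters.

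Main effects alone do little for the sex-by-dose test. So also pre-specify a sensitivity analysis for Hypothesis 1B that adds daily smoking by dose and race by dose, in the same dose form as the sex-by-dose term. That costs 3 further parameters if dose is linear, or 3 x 4 = 12 if it is categorical with five levels. Give a rule for collapsing race categories if cells are sparse.

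A sentence on how the matching is done, and how it is kept up after exclusions and replacements, would complete the change. Both variables are already created for the stratification, so no data collection, visits or subjects are added. This is a free improvement.

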## **9. Selection:**

Male and female smokers will be recruited from the New Haven area through newspaper advertisements and fliers. We will recruit both veterans and non-veterans since there are not enough veterans in our area who meet the inclusion criteria for the study. Interested subjects will have the study described over the telephone and will be asked to answer a brief tobacco use history and medical screening questionnaire. If subjects are eligible for the study based on the telephone screening, they will then be invited to come to the clinic for an initial screening evaluation. The initial screening evaluation will include the following: a) obtaining an informed consent; b) smoking history and assessment of nicotine dependence based on the Fagerstrom Test of Nicotine Dependence (FTND); and c) a urine semi-quantitative cotinine level to confirm active smoking status at study entry..

If subjects are eligible based on the stratification procedure, they will be invited to participate in a second evaluation, which will include: a) complete physical and psychiatric examination including the structured clinical interview (SCID) for DSM-V; b) laboratory examination including CBC, ALT, AST, alkaline phosphatase, glucose, BUN, creatinine c) DNA; d) urine analysis, drug screening, and for women, urine pregnancy test. The laboratory test results will be part of the patients' medical record at the VA Hospital located on the CPRS system, as well as in the subject's research chart; and e) ECG.

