## **11. Research Plan:**

### **A. Overview**

This will be a double-blind, placebo-controlled study, with 72 LITS (36 male and 36 female smokers) participating in five experimental sessions. All sessions will be conducted following overnight abstinence to control for recent nicotine intake. The lab sessions will be at least 24 hours apart to minimize carryover nicotine effect between sessions. In each experimental session, subjects will be randomly assigned to one of the five doses of nicotine (0.0125, 0.025, 0.05, 0.1 and 0.2 mg/70 kg or about 0.18, 0.36, 0.7, 1.4 and 2.8  $\mu$ g/kg). At the beginning of each experimental session, subjects will first sample the assigned nicotine dose and placebo (saline) condition that are randomly labeled as A or B. Beginning 15 minutes after the second sample dose, subjects will have the opportunity to choose between drug A or B every 15 minutes, for a total of ten opportunities over a 165-minute period. Immediately after subjects make their choice, drugs will be administered over 30 seconds using an infusion pump. The main outcome measure will be the number of nicotine self-administrations for each nicotine dose. The parameters of this nicotine self-administration procedure were based on our previous study (Sofuoglu et al. 2008a).

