## **B. Medical Monitoring and Safety**

Subjects will be given a thorough physical examination prior to entry in the study. For nicotine administration sessions, a physician will be present and subjects will be attached to a cardiac monitor as well as a blood pressure and heart rate monitoring device. An IV catheter will be in place throughout the session. Subjects will be administered nicotine only if the systolic blood pressure is <150 mmHg and heart rate is <100 beats/minute. Subjects will be terminated from the study if the blood pressure at any time is >170/110 mm Hg, the heart rate is >120 beats/min, or if they develop signs and symptoms compatible with nicotine toxicity. Subjects will remain in the laboratory for at least an hour after the last nicotine administration. These procedures have been developed as part of our IND for IV nicotine.

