### Biochemical

1) Alveolar carbon monoxide: The CO measurement taken before the sessions will help to verify compliance with smoking abstinence. CO readings  $\leq$  8ppm will be used to verify compliance with overnight smoking as recommended by the SRNT Subcommittee on Biochemical Verification (Benowitz et al. 2002).

2) Serum estradiol and progesterone analysis (females only): Serum estradiol and progesterone levels will be measured before each lab session for use as covariates in our analysis, since female sex hormones may contribute to sex differences in nicotine responses (Smith et al. 2006; Sofuoglu et al. 2001; Zubieta et al. 2002).

4) Plasma/urine cotinine, 3-hydroxycotinine (3-HC), and nicotine levels: Plasma/urine samples of cotinine will be taken at intake to quantify the level of nicotine intake of the subjects. 3-HC is the main metabolite of cotinine and the ratio of 3-HC/cotinine, also known as the nicotine metabolite ratio, reflecting the activity of cytochrome P450 (CYP2A6) and thus, the rate of nicotine clearance. Plasma nicotine levels will also be measured before each session to ensure overnight abstinence from smoking. Assays for nicotine, cotinine, and 3-HC levels will be performed in [name] laboratory. Briefly, nicotine, cotinine and 3-HC are measured using HPLC coupled to tandem mass spectrometry (LC/MS/MS) employing stable isotope labeled internal standards as previously described.

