## **E. Study Procedures**

**Session procedures:** Before the test sessions, smokers will be required to abstain from smoking for 10 h, which will be verified by expired air CO levels  $\leq 8$  ppm (Benowitz et al. 2002). Subjects will be asked to refrain from consuming alcoholic beverages and drugs during study participation, which will be verified by a urine drug quick test. If results indicate non-compliance with these study procedures, subjects will be discharged from the study. Subjects will be instructed to drink their typical amount of caffeinated beverages in the morning to minimize caffeine withdrawal, which could confound the study measures. Subjects will be instructed not to eat for four hours before the lab sessions to reduce the chance of vomiting. A light lunch will be provided at the end of each experimental session.

**Medical monitoring:** Subjects will be given a thorough physical examination prior to entry in the study. For nicotine administration sessions, a physician will be present and subjects will be attached to a cardiac monitor as well as a blood pressure and heart rate monitoring device. An IV catheter will be in place throughout the session. Subjects will be administered nicotine only if the systolic blood pressure is  $<150$  mmHg and heart rate is  $<100$  beats/minute. Subjects will be terminated from the study if the blood pressure at any time is  $>170/110$  mm Hg, the heart rate is  $>120$  beats/min, or if they develop signs and symptoms compatible with nicotine toxicity. Subjects will remain in the laboratory for at least an hour after the last nicotine administration. These procedures have been developed as part of our IND for IV nicotine.

TABLE 1. SCHEDULE OF EVENTS: EXPERIMENTAL SESSION\*

Minutes	Time point	Measures and Events
0 Min	1	HR/BP, DEQ, IV nicotine or saline administration A (sampling) CO, HR/BP, EKG, M
1 Min	2	HR/BP, DEQ
2 Min	3	HR/BP,
3 Min	4	HR/BP, DEQ
5 Min	5	HR/BP, DEQ
15 Min	6	HR/BP, DEQ IV nicotine or saline administration B
16 Min	7	HR/BP, DEQ
17 Min	8	HR/BP
18 Min	9	HR/BP, DEQ
20 Min	10	HR/BP, DEQ
30 Min	11	HR/BP, DEQ IV Choice Sampling Option 1
31 Min	12	HR/BP, DEQ
32 Min	13	HR/BP
33 Min	14	HR/BP, DEQ
35 Min	15	HR/BP, DEQ
45 Min	16	HR/BP, DEQ IV Choice Sampling Option 2
46 Min	17	HR/BP, DEQ
47 Min	18	HR/BP
48 Min	19	HR/BP, DEQ
50 Min	20	HR/BP, DEQ
60 Min	21	HR/BP DEQ IV sampling Option 3
61 Min	22	HR/BP, DEQ
62 Min	23	HR/BP
63 Min	24	HR/BP, DEQ
65 Min	25	HR/BP, DEQ

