## **14. Safety**

Prior to initiating any research activity, each subject must give informed consent. Before the study, the subjects will be informed about all potential risks of the study. Our inclusion and exclusion criteria will be applied by experienced professionals who will be carefully trained and monitored in order to accept only appropriate subjects into the study. Thus, effective screening will exclude subjects who would be placed at a greater risk. Eligibility is determined by the medical and psychiatric history, drug use history, the physical examination, and the laboratory studies done prior to beginning this research protocol.

For nicotine administration sessions, a physician will be present and subjects will be attached to a cardiac monitor as well as a blood pressure and heart rate monitoring device. An IV catheter will be in place throughout the session. Subjects will be administered nicotine only if the systolic blood pressure is <150 mmHg and heart rate is <100 beats/minute. Subjects will be terminated from the study if the blood pressure at any time is >170/110 mm Hg, the heart rate is >120 beats/min, or if they develop signs and symptoms compatible with nicotine toxicity. Subjects will remain in the laboratory for at least an hour after the last nicotine administration. These procedures have been developed as part of our IND for IV nicotine.

Confidentiality will be protected by having records identified by code number only with the master list including names kept in a sealed envelope in a locked file in the Principal Investigator's office and by the pharmacy. Subjects will be given telephone numbers to call in case of emergency, 24 hours a day.

**14.1 Potential benefits of the proposed research to the subjects and others.** There will be no direct benefit to subjects participating in this study. However, subjects will receive complete medical and psychological evaluation. Cigarette smokers will be given anti-smoking literature and treatment resources will be provided for smoking cessation.

**14.2 Importance of the knowledge to be gained.** This proposed study may help to develop new and more effective tobacco control policies. We believe that the risk/benefit ratio for this study is acceptable, and that the benefits of the proposed studies outweigh the potential risks to subjects.

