- All paper documents will be locked in an approved file cabinet with only members of the research team having access.

Electronic:

- All information in electronic form will be stored on VA servers behind the VA firewall.
- All portable media will meet or exceed FIPS 140-2 compliance and encryption. And will be approved in writing by the Information Security Officer.

The location(s) where information will be stored is (are) Building 35, rooms 19 and 39

The people or agencies that will have access to the information are the study investigators.

No information related to this research will be released to any third party or disclosed outside of the VHA – except as required or permitted by law.

Research records will have identifiers removed and will be stored with a code number linked to subjects. The code will not be derived from any personal identifiers. The key to the code will be kept in a locked file cabinet, located in Bldg 35, room 19. Subjects' identity will not be revealed in any reports or publications resulting from this study.

**17. Location of Study:** This study will be conducted in Ward G9W (the Biostudies Unit) located in Building 1 at the West Haven VA Medical Center.

**18. Payment:** Subjects will be paid \$30 for participating in the screening and \$130 for each of the 5 lab sessions and \$20 for transportation for each of the 5 test sessions. If the subjects choose to terminate a session prematurely, or a session is terminated early for medical reasons, they will receive full payment for that day. If they become ineligible to continue in the study due to non-compliance with study procedures, they will only be paid for the portions of the study in which they have participated. Subjects may also earn \$20 for referring people they know who also smoke cigarettes and are eligible for study participation. A contingency payment of \$20 will also be given for transportation for a visit that wasn't fulfilled in the outlined time frame within the protocol. Subjects may be paid up to \$780 if all parts of the study are completed.

**19. Funding Source:** An RO1 grant from NIDA (pending).

**20. Duration:** The new study design will take approximately 3 years to complete.

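### In the legible text, women are tested for pregnancy once, at screening; no test is named before the five IV nicotine sessions, and no dosing or stopping rule mentions pregnancy (minor)

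*Combined protocol and SAP*

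**What the plan says.** Inclusion criterion 7 in section 7 (Subjects) requires women to be "not pregnant as determined by pregnancy screening, nor breast feeding, and using acceptable birth control methods". Section 9 (Selection) supplies the test: the second screening evaluation includes "urine analysis, drug screening, and for women, urine pregnancy test". Section 14 (Safety) bases eligibility on history, examination and "the laboratory studies done prior to beginning this research protocol".

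Sessions follow later. There are five, and section 11.A says: "The lab sessions will be at least 24 hours apart to minimize carryover nicotine effect between sessions". The checks tied to them are set out in two places:

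- Section 11.C, Biochemical: CO, plasma nicotine and, for women, "Serum estradiol and progesterone levels will be measured before each lab session". The stated use of the hormone levels is as covariates in the analysis.
- Section 11.E, Session procedures: CO again, and abstinence from alcohol and drugs, "which will be verified by a urine drug quick test". How often that urine test is done is not stated. Subjects whose results show non-compliance are discharged.

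The rule for giving nicotine appears in sections 11.B, 11.E and 14: "Subjects will be administered nicotine only if the systolic blood pressure is <150 mmHg and heart rate is <100 beats/minute". Alongside it, a subject is terminated for blood pressure above 170/110 mm Hg, heart rate above 120, or signs of nicotine toxicity.

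**The concern.** A single test at screening shows a woman's status on that day, within the limits of what a urine test can detect. Dosing comes afterwards, on five separate days. If she conceives between screening and a session, or if the pregnancy was too early to show at screening, no step in the legible plan would bring it to light before the next infusion.

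What is at stake is participant safety in women aged 18 to 35. The protocol keeps pregnant women out at entry, and its definition of a serious adverse event in section 14.3 includes congenital abnormality. It would be consistent to look again at the time of dosing. The consequence should not be inflated: these women already smoke, the study doses are low, and no estimate, test or sample size figure depends on this.

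**Working it through.** The plan gives no figure on this point to reproduce. The check is a reading of each place where a pregnancy test or rule could stand, followed by simple counts of scale.

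**Places compared**

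| Place | What it names | Pregnancy test or rule? |
|---|---|---|
| Section 7, criterion 7 | Entry condition, met by screening | Refers to screening |
| Section 9, second evaluation | Urine pregnancy test | Yes, once |
| Section 11.C, Biochemical | CO; estradiol and progesterone; cotinine, 3-HC, nicotine | No (item 3 absent) |
| Section 11.E, Session procedures | CO, urine drug test, discharge for non-compliance | No |
| Table 1 | Vital signs, ratings, CO, EKG | None legible (time-0 row cut off) |
| Sections 11.B, 11.E and 14, dosing and termination | Blood pressure, heart rate, toxicity | No |

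The hormone assays do not fill the gap. They are taken for the analysis, and no result threshold or dosing rule is attached to them.

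Table 1 is weak evidence either way. Its legible rows and abbreviation key also omit the urine drug test, plasma nicotine and the hormone assays, all of which the prose names. The finding therefore rests on the prose of sections 11.C and 11.E.

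**Time between screening and dosing.** Five sessions have four gaps of at least 24 hours, so the shortest span from first to last session is 4 × 24 = 96 hours. No longest span can be read. Section 18 (Payment) mentions a visit not "fulfilled in the outlined time frame within the protocol", so a limit may exist, but no legible text gives it.

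**Scale**

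- Female completers 36 (section 7), sessions 5 (section 11.A): 36 × 5 = 180 sessions. Women who are dosed but do not complete add to this.
- Each session has one nicotine sample and up to ten nicotine choices. For one session, the minimum is 1 × 0.0125 = 0.0125 mg/70 kg and the maximum is (1 + 10) × 0.2 = 2.2 mg/70 kg.
- Sum of the five doses: 0.0125 + 0.025 + 0.05 + 0.1 + 0.2 = 0.3875 mg/70 kg.
- All five sessions:
  - samples only: 1 × 0.3875 = 0.3875 mg/70 kg
  - half of the choices for nicotine: (1 + 5) × 0.3875 = 2.325 mg/70 kg
  - every choice for nicotine: (1 + 10) × 0.3875 = 4.2625 mg/70 kg
- Section 5 (Background) equates 5 mg of nicotine a day with about 5 cigarettes, which is the eligibility ceiling. For a 70 kg woman, 4.2625 / 5 = 0.85. The largest possible total over all five sessions is thus about 85% of one day's intake at that ceiling. It applies only to a woman already pregnant at session 1 who chooses nicotine 50 times out of 50. The comparison ignores cigarettes forgone during the abstinence and the session.

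**The case against.** **The text is incomplete where a session test would be listed.** The biochemical list runs 1, 2, 4, and the missing item follows directly after the female-only assay taken before each session. The time-0 row of Table 1, where pre-infusion checks belong, breaks off after EKG and a single letter. There is no section 8, and the consent pages are not available. A reader might infer that the protocol has no session test at all. The documents do not support that; they support only that none is named in what can be read. This objection stands and limits the finding. It does not reach the dosing and termination statements, which are legible in three places and attach no consequence to a pregnancy.

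**Criterion 7 is an entry criterion.** A reader might infer that dosing a woman who conceives later would breach it. It would not: the screening test satisfies the criterion, and nothing printed requires it to be met again at each session.

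**The blood pressure and heart rate sentence is not the whole gate.** A reader might take it as the only condition for dosing. Section 11.E also discharges subjects on CO or urine drug results, and that rule lies outside the sentence. Silence there is therefore weaker evidence than it first seems. The discharge rule does not mention pregnancy either, so the gap remains.

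**Other safeguards exist.** Birth control is required, a physician attends each session, the investigator may withdraw a subject, and the DSMB meets three times a year. Birth control lowers the chance of pregnancy. The others can act on a pregnancy only once someone knows of it. None is a test.

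**The risk is not quantified.** This is correct. With the longest interval unreadable, no probability of an undetected pregnancy can be given, and the sessions could be finished within days.

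**Conclusion.** The point holds as a minor gap in continued safety checking. In the legible text, pregnancy is tested once, before dosing, and no dosing, termination or discharge rule mentions it. A pregnancy that arises or becomes detectable after screening could go unnoticed through one or more IV nicotine sessions, and through all five only if conception preceded the first.

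Its size is about 180 female sessions without a named test, with added nicotine per session between 0.0125 and 2.2 mg/70 kg. Neither figure is a risk estimate. No endpoint, estimate or power figure changes.

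The conclusion assumes that the cut-off Table 1 row and the absent biochemical item do not list a session test. If they do, what remains is the missing instruction on what to do with a positive result.

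**What to change.** First check the full Table 1 time-0 row and biochemical item 3.

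If no session test is listed, add to section 11.E and Table 1 a negative urine pregnancy test for women before the first infusion of each session. Use the drug-test urine where it is collected that day, and a small separate sample otherwise. In sections 11.B, 11.E and 14, state that a positive result stops dosing. If a session test is already listed, add only that stop-dosing line.

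The cost is about 180 dipsticks for 36 female completers (more with non-completers), a line on the session form, a few minutes per female session, and a consent update if per-session testing is not already described. A dipstick can still miss a very early pregnancy; repeating it gives later sessions a chance to catch it.
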